6.2.1.1 Medical history

A medical history should be obtained by the investigator or qualified designee. It includes all active diseases and diseases diagnosed that are clinically significant, as determined by the investigator, including but not limited to history of cigarette use, alcohol use, surgery, and drug allergy. All autoimmune diseases should be documented, regardless of the date of onset.

6.2.1.2 Prior medications

All medications (including over-the-counter supplements) used within 30 days prior to the first dose of study treatment, including any washout requirements specified in the protocol, will be reviewed by the investigator or qualified designee and should be documented.

6.2.1.3 Concomitant medications

The investigator or qualified designee will document all the medications used throughout the trial (from the signing of the ICF to the safety follow-up). Concomitant medications related to SAEs and irAEs should be documented.

6.2.2 Baseline (prior to Day 1 of Cycle 1)

- Recording the vital signs
- Weight (no need to repeat if done previously within 7 days prior to the first dose)
- ECOG PS (no need to repeat if done previously within 7 days prior to the first dose)
- 12-lead ECG
- AE evaluation
- Concomitant medications Thyroid function
- Complete blood count/blood biochemistry
- Coagulation function
- Blood pregnant test
- HBV DNA and/or HCV RNA (if applicable)

6.2.3 Tumor imaging evaluation (if applicable), Tumor biopsy (if applicable), Treatment visits

- Recording the vital signs
- Weight
- Physical examination
- ECOG PS
- 12-lead ECG
- Complete blood count/blood biochemistry
- Urine or Blood pregnant test (if applicable, every other cycle from Cycle 2 onwards))
- Thyroid function (every other cycle from Cycle 2 onwards)
- AE evaluation
- Concomitant medications
- EQ 5D-5L (if applicable)
- EORTC QLQ-C30 (if applicable)
- PRO-CTCAE (if applicable) Tumor imaging evaluation (if applicable)

- Fresh tumor tissue (C3D1) (optional if clinically feasible)
- Administration of study drugs (tumor imaging evaluation should be performed prior to administration)
- Blood sampling for biomarkers and PK sampling (if applicable)
- Survival status

Refer to [**Table 1**](#) for the study schedule during the treatment.

Refer to Sections [7.1](#), [7.2](#), 7.3 and [7.4](#) for details regarding tumor imaging evaluation, safety evaluation, biomarker sampling, and PK sampling, respectively.

6.2.4 End-of-treatment visits

The following should be completed within \pm 7 days after confirming the end of treatment:

- Recording the vital signs
- Physical examination
- Weight
- ECOG PS
- 12-lead ECG
- Complete blood count/blood biochemistry/routine urinalysis
- Thyroid function
- Pregnancy test (if applicable)
- Blood sampling for biomarkers (if applicable)
- Tumor imaging evaluation (if applicable)
- AE evaluation
- Concomitant medications
- Survival status
- Subsequent anti-tumor therapy
- EQ 5D-5L
- EORTC QLQ-C30

- PRO-CTCAE

6.2.5 Safety follow-up

The safety follow-up will be performed at the 30th day (\pm 7 days) and 90th day (\pm 7 days) after the last dose and will include the following procedures:

- ECOG PS
- 12-lead ECG (for the 30-day safety follow-up only)
- Complete blood count/blood biochemistry (for the 30-day safety follow-up only)
- AE evaluation
- Concomitant medications (for the 30-day safety follow-up only)
- Document subsequent anti-tumor therapy
- PRO-CTCAE (for the 30-day safety follow-up only)
- Survival status

If the safety follow-up is less than 7 days after the end-of-treatment visit, then the safety follow-up may be replaced by the end-of-treatment visit and does not need to be repeated.

If the subject initiates a new anti-tumor therapy within 30 days after the last dose, then the safety follow-up must be performed before initiation of the new therapy.

6.2.6 Survival follow-up

After completing the safety follow-ups, the subject should be contacted (telephone visits are allowed) once every 60 days (\pm 7 days) to obtain the survival information, any subsequent systemic anti-tumor therapy, and PD information. Long-term follow-up should be continued until death or 3 years after last patient enrolled.

Subsequent anti-tumor therapy

The investigator or qualified designee will collect all the information about new anti-tumor therapies initiated after the last dose of the study drugs and the corresponding efficacy. If the subject initiates a new anti-tumor therapy within 30 days after the last dose, then the safety follow-up must be performed before initiation of the new therapy.

The subject should be followed for survival after initiation of a new anti-tumor therapy. Refer to Section [6.2.6](#) – Survival follow-up for details regarding survival follow-up.

6.2.7 Unscheduled visits

Unscheduled visits may be performed if requested by the subject or investigator. The investigator will carry out relevant examinations based on the subject's status, which includes but is not limited to the vital signs, targeted physical examination, ECOG PS, complete blood count/blood biochemistry/routine urinalysis, and tumor imaging evaluation.

7 Study Evaluation

7.1 Efficacy Evaluation

Tumor evaluations will be performed based on RECIST v1.1. Refer to Appendix [3](#) for the evaluation methods.

All the decisions made during the study will be based on the imaging evaluations by the independent and investigator radiology review, subject's clinical status, and relevant examination results.

7.1.1 Tumor imaging and disease evaluations

Tumor imaging examinations usually include contrast-enhanced CT or MRI of the chest, abdomen, and pelvis. Contrast-enhanced MRI should also be performed on the brain at baseline for subjects with signs and symptoms of CNS metastasis. The imaging method should be consistent for a given subject during the trial.

During the screening, the investigator of the study site will confirm the presence of measurable lesions based on RECIST v1.1 to determine the eligibility of the subject. According to RECIST v1.1, a maximum of 5 lesions in total and 2 lesions per organ will be recorded.

7.1.2 Tumor imaging during the study

The imaging method used for the evaluation of tumor burden during each visit should be the same as the one used at baseline. Other affected sites should be examined based on the signs and symptoms of each subject. Baseline evaluation will be conducted within 28 days prior to the first dose of the study treatment, which means the investigator can evaluate the imaging results within 28 days prior to the enrollment.

After the first dose of study treatment, tumor imaging evaluation will initially be performed once Q6W (\pm 7 days) and Q9W (\pm 7 days) starting from Cycle 7, until initiation of a new anti-tumor

therapy, PD (at 12W or after), withdrawal of informed consent, lost to follow-up, death, or completion of the study (whichever comes first).

Patients who have radiographic PD will be allowed to continue therapy if clinically stable till next scheduled scans. If PD is confirmed on the next scan, patient will discontinue therapy. For certain cases which PD cannot be determined, especially on those with equivocal non-target lesions enlargement or equivocal new lesions, the treatment may be continued until signs of clinical instability develop or when PD is confirmed by the investigator in the next scheduled scan. Once PD is confirmed, the disease progression date will be recorded as the date when the suspected PD was initially observed. Definition of clinical stability is as follows:

- Absence of clinically significant signs and symptoms suggesting PD (including worsening laboratory values);
- No reduction in ECOG PS score;
- No rapid PD;
- Absence of rapid progression of disease or progressive tumor at critical anatomical sites (e.g. spinal cord compression) that requires urgent medical interventions.

Tumor evaluations should be performed as scheduled and should not be delayed due to treatment delays, holidays, or any other reasons.

Further tumor evaluations are not required for subjects who discontinue the treatment due to radiographic PD.

For subjects who discontinue the treatment for reasons other than radiographic PD, tumor evaluation should be performed Q12W (\pm 7 days) until one of the followings occurs: start of new anti-tumor therapy, PD, withdrawal of informed consent, or death. A scan at the end of the treatment is not mandatory if it were less than 4 weeks after the last tumor evaluation.

If the subject has confirmed or suspected bone metastatic lesion(s) present at baseline, a contrast enhanced PET/CT can be used for efficacy assessment.

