4.1 Inclusion Criteria

1. Histopathologically confirmed unresectable, locally advanced, recurrent or metastatic UPS or high-grade myxofibrosarcoma.
2. Refractory or intolerant to at least one line of systemic chemotherapy. Patient ineligible for cytotoxic chemotherapy are eligible.
3. Aged \geq 18.
4. ECOG PS of 0 or 1.
5. Subject must be unsuitable for definitive treatment, such as definitive chemoradiotherapy and/or surgery.
6. Could provide archival or fresh tissues for correlative analysis.
7. Have at least one measurable lesion as per RECIST v1.1.
8. Adequate organs and bone marrow functions, as defined below:

- 1) Complete blood count: absolute neutrophil count (ANC) $\geq 1.0 \times 10^9/L$, platelet (PLT) count $\geq 75 \times 10^9/L$, hemoglobin (HGB) $\geq 8.0 \text{ g/dL}$. Note: Subjects cannot receive blood transfusion, erythropoietin (EPO), or Granulocyte-colony stimulating factor (GSF) within 7 days prior to the blood collection.
- 2) Hepatic function: total bilirubin (TBIL) $\leq 1.5 \times$ upper limit of normal (ULN), alanine aminotransferase (ALT) and aspartate aminotransferase (AST) $\leq 2.5 \times$ ULN in subjects without hepatic metastasis; TBIL $\leq 1.5 \times$ ULN, ALT and AST $\leq 5 \times$ ULN in subjects with hepatic metastasis. Exception: Patients with known Gilbert disease: serum bilirubin level $\leq 3 \times$ ULN.
- 3) Renal function: urine protein $< 2+$ from random sample or $< 1 \text{ g}$ from 24-hour urine collection, and creatinine clearance rate (Ccr) $\geq 60 \text{ mL/min}$ by Cockcroft-Gault formula:

$$\text{Female: } Ccr = \frac{(140 - \text{age}) \times \text{weight(kg)} \times 0.85}{72 \times \text{serum creatinine(mg/dL)}}$$

$$\text{Male: } Ccr = \frac{(140 - \text{age}) \times \text{weight(kg)} \times 1.00}{72 \times \text{serum creatinine(mg/dL)}}$$

- 4) Adequate coagulation function, defined as international normalized ratio (INR) ≤ 1.5 or prothrombin time (PT) $\leq 1.5 \times$ ULN; if the subject is receiving anticoagulant therapy, the results of coagulation tests need to be within the acceptable range for anticoagulants.

9. Expected survival $\geq 12 \text{ weeks}$.
10. Subject (female subjects of childbearing age or male subjects whose partners are of childbearing age) must take effective contraceptive measures during the entire course of the trial and until 180 days after the last dose (see Section 4.3).

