4.4 Criteria for Discontinuation/Withdrawal

4.4.1 Treatment discontinuation

Treatment discontinuation is not the same as withdrawal from the study. Since data on some clinical events after treatment discontinuation may be important to the study, these data must be collected until the subject's last scheduled visit, even if the treatment has already been discontinued.

A subject must discontinue the treatment in the case of any of the following, but can continue to be monitored during the study:

- Disease progression as per RECIST v1.1 at 12 W or after
- Treatment discontinuation required by the subject or his/her legal representative;
- Occurrence of an AE that requires discontinuation due to protocol-specified reasons (refer to Section 5.2);
- Onset of another malignant tumor that requires active treatment;
- Onset of a concurrent disease that interferes further treatment;
- Positive serum pregnancy test results;
- Poor compliance of the subject;
- Inappropriate to continue participating in the study when continued participation would result in unacceptable risk to the subject, as determined by the investigator and/or sponsor;
- Completion of 24-month of treatment with the study drugs.

All the visits and procedures presented in the study schedule ([Table 1](#)) should be completed for subjects who discontinued treatment but continue to be followed.

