7.2.1.3 ECOG PS

The investigator or qualified designee will evaluate PS during screening, prior to administration on Day 1 of each treatment cycle, during the end-of-treatment visit, and during safety follow-up in accordance with the instructions in the Schedule of Visits.

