Appendix 2: ECOG PS

Score	Performance Status
0	Fully active, able to carry on all pre-disease performance without restriction
1	Restricted in physically strenuous activity but ambulatory and able to carry out work of a light nature or office work
2	Ambulatory and capable of all selfcare but unable to carry out any work activities; up and about more than 50% of waking hours
3	Capable of only limited selfcare; confined to bed or chair more than 50% of waking hours
4	Completely disabled; cannot carry on any selfcare; totally confined to bed or chair
5	Death

References

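### The ECOG condition in the Section 7.1.2 definition of clinical stability points the wrong way: it passes every worsening and fails only an improvement

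*Combined protocol and SAP*

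**What the plan says.** Section 7.1.2 permits treatment past progression: "Patients who have radiographic PD will be allowed to continue therapy if clinically stable till next scheduled scans". If progression is then confirmed on the next scan, therapy stops. Where progression cannot be determined, the same notion of stability acts as the stop signal, since "the treatment may be continued until signs of clinical instability develop" or until the next scheduled scan confirms progression.

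Clinical stability is defined by four bullets. Three concern signs, symptoms and laboratory values that suggest progression, the pace of progression, and tumour at critical sites. The fourth is "No reduction in ECOG PS score".

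Section 7.2 refers the reader to Appendix 2 for the ECOG criteria. That scale starts at 0 for a fully active person and reaches 4 for one who is "Completely disabled; cannot carry on any selfcare; totally confined to bed or chair"; 5 is death. Section 4.1 restricts entry to "ECOG PS of 0 or 1".

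**The concern.** On this scale functional decline is a rise in score. A bullet that forbids a fall therefore forbids improvement and says nothing about decline. It names the score rather than performance status or function, so its literal meaning is clear, and it is the opposite of what a stability criterion needs.

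The text is operative: it helps decide who may be dosed after radiographic progression. ECOG is also the only graded functional measure among the four bullets. Worded this way, it cannot screen out a subject whose function is deteriorating, which is its evident purpose.

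**Working it through.** The plan gives no figure on this point. The check is to apply the bullet literally to every possible change in score, and then to see what dosing the definition controls.

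**Inputs**
- Entry score: 0 or 1 (Section 4.1).
- Living states: 0 to 4 (Appendix 2).
- Dose: 200 mg every 21 days from Day 1 (Section 5, Table 3).
- Scans: every 6 weeks, then every 9 weeks from Cycle 7 (Sections 3.1 and 7.1.2). Table 1 places the first two at Days 43 and 85.
- Order on a scan day: "tumor imaging evaluation should be performed prior to administration" (Section 6.2.3).

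**Direction of the rule**

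Let *b* be the reference score and *s* the new score.
- As written: pass if *s* ≥ *b* (no reduction).
- Reversed: pass if *s* ≤ *b* (no increase).

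From baseline 0 the worsenings are to 1, 2, 3 or 4, which is 4. From baseline 1 they are to 2, 3 or 4, which is 3. The total is 4 + 3 = 7. The only improvement is from 1 to 0. Two states are unchanged.

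| Change from entry score 0 or 1 | Number | Pass as written | Pass if reversed |
|---|---|---|---|
| Worsening | 7 | 7 | 0 |
| Improvement | 1 | 0 | 1 |
| Unchanged | 2 | 2 | 2 |

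The bullet does not say which earlier assessment is the reference. If any score from 0 to 4 may be the reference, there are 10 worsenings, 10 improvements and 5 unchanged pairs. As written, 10 of 10 worsenings and 0 of 10 improvements pass; reversed, 0 of 10 and 10 of 10. Unchanged pairs pass under both. The inversion does not depend on the reference.

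**Exposure the definition governs**

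Nominal dosing days are 1 + 21*k*: 1, 22, 43, 64, 85, 106, 127, 148, 169, 190.
- Progression on the Day 43 scan, next scan Day 85: doses on Days 43 and 64, so 2 × 200 mg = 400 mg.
- Progression on the Day 85 scan, next scan Day 127: doses on Days 85 and 106, so 2 × 200 mg = 400 mg.
- Progression on the Day 127 scan, next scan 9 weeks later on Day 127 + 63 = 190: doses on Days 127, 148 and 169, so 3 × 200 mg = 600 mg.

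Only the first line applies without qualification. Section 4.4.1 requires discontinuation for "Disease progression as per RECIST v1.1 at 12 W or after", so the second and third lines arise only if Section 7.1.2 is taken to override it.

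**The case against.** The strongest reply is that this is a drafting slip nobody would follow. The bullet sits in a list that defines stability, next to conditions about symptoms and rapid progression. No investigator would stop a subject for improving from 1 to 0 or call a change from 1 to 3 stable. That is probably how most sites would read it, and it limits the likely harm. It does not make the text right, and compliance is monitored against the text.

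Second, the definition requires all four bullets. A subject whose ECOG rises to 3 or 4 at progression would very likely also fail the bullet on signs and symptoms. Continuation is permitted, not required. Investigators may stop treatment for other reasons (Section 3.1), must stop it for unacceptable risk (Section 4.4.1), and are to weigh clinical status in decisions (Section 7.1). All of this stands, which is why the point is confined to the one bullet.

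Third, the counts describe score pairs, not patients, and the doses are what any subject treated past progression would receive. This is also right. The extra exposure due to the wording falls only on subjects whose ECOG worsens, who pass the other three bullets, and whose investigator applies the text literally. The documents give no basis for sizing that group, and it may be empty. The dose counts also ignore the ±7-day scan window.

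Fourth, reversing the direction still leaves the reference visit unstated. That is a fair criticism, and the fix below deals with it.

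**Conclusion.** The concern holds. The ECOG bullet is inverted relative to Appendix 2, and no other part of the protocol corrects it. From entry ECOG 0 or 1, taking baseline as the reference, it passes 7 of 7 worsenings and fails the 1 improvement; reversing it gives the intended result in all 8 cases.

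The practical reach is narrow. The definition controls 2 doses (400 mg) after progression at the week-6 scan on the nominal schedule, and more only if Section 7.1.2 prevails over Section 4.4.1. Other safeguards remain in place.

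Nothing statistical changes. Confirmed progression is dated to the scan where it was first suspected, the response criteria in Appendix 3 do not use ECOG, and the design's error rates are untouched. It is a wording error in a treatment-continuation safety rule and should be fixed.

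**What to change.** Replace the bullet with: *No increase (worsening) in ECOG PS score*. In the same line, state the reference assessment, for example baseline or the last assessment before the scan showing progression.

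The cost is a one-line amendment. Section 7.2.1.3 already provides the data: "The investigator or qualified designee will evaluate PS during screening, prior to administration on Day 1 of each treatment cycle". No new visit, assessment or subject is needed, and the sample size is unchanged.

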7.2 Safety Evaluation

The investigator or qualified designee should evaluate each subject, as specified in the schematic of the study design, to identify the potential new or worsening AEs. Safety evaluations can be performed more frequently if clinically indicated. AEs are graded and documented according to

NCI CTCAE v5.0 during the study and follow-up. Toxicities will be characterized by severity grade, attribution/causality, and actions taken with the study treatment.

All AEs with unknown causes after exposure to the study treatment must be evaluated to determine whether the event is potentially immune-related.

Refer to Sections [8.2](#) and [8.3](#) for details regarding AE evaluation and documentation.

Refer to the schedule of visits in [Table 1](#) for the timing of the evaluations. Refer to Appendix [2](#) for ECOG PS criteria.

7.2.1 Physical Examination

7.2.1.1 Comprehensive physical examination

A comprehensive physical examination will be performed by the investigator or designee during the screening. All the clinically significant abnormalities should be documented in the disease history. After the first dose of study treatment, any new clinically significant abnormalities should be documented as AEs.

7.2.1.2 Targeted physical examination

In cycles where a comprehensive physical examination is not required by the study protocol, targeted physical examination should be performed by the investigator or qualified designee if clinically indicated. The examination should be scheduled prior to administration on Day 1 of each treatment cycle. All of the clinically significant abnormalities should be documented as AEs.

7.2.1.3 ECOG PS

The investigator or qualified designee will evaluate PS during screening, prior to administration on Day 1 of each treatment cycle, during the end-of-treatment visit, and during safety follow-up in accordance with the instructions in the Schedule of Visits.

7.2.1.4 Vital signs

Vital signs will be examined in accordance with the schedule of visits in [Table 1](#), including temperature, pulse, respiratory rate, and blood pressure. The time and date of measurement should be documented in the appropriate section of the database. Temperature, pulse, respiratory rate, and blood pressure should be measured prior to the administration of study drugs.

7.2.1.5 12-lead ECG

A resting 12-lead ECG will be performed at the local laboratory in accordance with the schedule of visits in [**Table 1**](#).

The subject must be resting in a supine position for at least 5 min prior to 12-Lead ECG. All the 12-lead ECG results should be recorded in the supine position. Further ECGs (or other related tests) should be performed if clinically indicated, such as a cardiac AE. The investigator should review the ECG on the day it is performed. The evaluation method should be consistent throughout the trial.

The investigator should evaluate all the ECGs as either normal, clinically significant abnormalities, or clinically insignificant abnormalities. If it is a clinically significant abnormality(s), the investigator should document an AE in the database.

7.2.2 Routine laboratory safety evaluations

See below for the specific laboratory procedures/evaluations. Refer to the Procedure Manual for the total amount of blood/tissues extracted/collected throughout the trial (from pre-trial to post-trial visits), including the amount of each subject's blood/tissues extracted/collected for each specimen type during each visit. Refer to the section on laboratory evaluations in the Schedule of Visits.

7.2.2.1 Laboratory safety evaluation (complete blood count, routine urinalysis, and blood biochemistry)

Refer to [**Table**](#) for laboratory tests including complete blood count, routine urinalysis, and blood biochemistry.

Table 6 Routine laboratory safety evaluation

Complete blood count	RBC, HGB, WBC, PLT, LYM, and ANC
Blood Biochemistry	TBIL, ALT, AST, ALP, ALB, TP, LDH, UREA, Cr, Na, K, Cl, Mg, Ca, P, amylase, and BG
Routine Urinalysis	PH, UWBC, UPRO, URBC, and UGLU
Thyroid Function	FT3, FT4, and TSH
Coagulation Function	PT and INR
Viral Serological Test	HBsAg, HBsAb, HBcAb, HCV antibody, HCV RNA, and HIV antibody

ALB = albumin; ALP = alkaline phosphatase; ALT = alanine aminotransferase; ANC = absolute neutrophil count; AST = aspartate aminotransferase; Cr = serum creatinine; BG = blood glucose; FT3 = free triiodothyronine; FT4 = free thyroxine; HBcAb = hepatitis B core antibody; HBeAb = hepatitis B e antibody; HBeAg = hepatitis B e antigen; HBsAb = hepatitis B surface antibody; HBsAg = hepatitis B surface antigen; HBV = hepatitis B virus; HCV = hepatitis C virus; HGB = hemoglobin; HIV = human immunodeficiency virus; INR = international normalized ratio; LDH = lactate dehydrogenase; LYM = lymphocyte count; PH = pH; PLT = platelet; PT = partial thromboplastin time; TBIL = total bilirubin; TP = total protein; TSH = thyroid stimulating hormone; RBC = red blood cell; UGLU = urine glucose; UPRO = urine protein; URBC = urine red blood cell; UREA = urea; UWBC = urine white blood cell; WBC = white blood cell.

